11.1.1.4. Statistical Methods - Primary Endpoint - Main Randomized Cohort

All subjects who are enrolled and randomized will be eligible for evaluation. Any events or hospitalizations occurring after enrollment but prior to the index procedure should be entered in the electronic data capture system.

Handling of dropouts and missing data will depend on their frequency and the nature of the outcome measure. Sensitivity analyses (e.g., tipping-point analysis) will be performed to assess the impact of subjects with inadequate follow-up (i.e., missing data) on the primary endpoint and to assess the robustness of the conclusion of the primary analysis. A sensitivity analysis of the primary endpoint, including events occurring after enrollment but prior to the index procedure, will be performed. Statistical models that account for censored data will be employed in appropriate circumstances (e.g., for time-to-event outcomes). Suspected invalid data will be queried and corrected in the database prior to statistical analysis. Additional information may be found in the SAP. Please also see Section **9.4**, Section **10.1**, and Section **10.2.1** regarding data collection and missing data.

11.1.2. ACURATE Prime XL Nested Registry Statistical Assessment

The statistical assessment for the ACURATE *Prime* XL Nested Registry is summarized in the sections below. Additional information may be found in the SAP.

11.1.2.1. Statistical Hypothesis - ACURATE Prime XL Nested Registry

The statistical hypothesis is that the mean aortic valve pressure gradient at 30 days post implant procedure is less than a performance goal (PG):

H₀: Gradient_{30D} \ge PG

H₁: Gradient_{30D} < PG

where Gradient_{30D} is the 30-day mean aortic valve pressure gradient for the ACURATE *Prime* XL valve and PG is 15 mmHg.

A one-sample *t*-test will be used to test the one-sided hypothesis at a significance level of 2.5%.

11.1.2.2. Sample Size Parameters for the ACURATE Prime XL Nested Registry

The sample size calculation is based on the following assumptions.

- Expected 30-day mean pressure gradient from ACURATE *Prime* XL = 10 mmHg
- Expected standard deviation = 7 mmHg
- PG = 15 mmHg
- Test significance level (α) = 0.025 (1-sided)
- Power > 90%
- Evaluable number of subjects = Minimum of 40 subjects
- Expected rate of attrition = 20% (8 subjects)
- Planned enrollment of 50 subjects
- The analysis population for the hypothesis testing will be the subject population implanted with the ACURATE *Prime* XL valve.

Note: The expected mean gradient is based on Boston Scientific data on file and published data for large-annulus CoreValve devices^{43,48,49}.

11.1.2.3. Success Criteria for the ACURATE Prime XL Nested Registry

If the *P* value from the one-sample *t*-test is < 0.025, the ACURATE *Prime* XL valve will be concluded to have a 30-day mean aortic valve pressure gradient < 15 mmHg. This corresponds to the one-sided upper 2.5% confidence bound of the observed 30-day mean aortic valve pressure gradient being < 15 mmHg.

11.1.3. Baseline Comparability

Baseline data will be summarized by treatment group for the randomized subjects (Main Randomized Cohort and Extended Durability Study) and separately for the Roll-In, ACURATE *Prime* XL Nested Registry, and CAS subjects. Subject demographics, clinical and neurological history, risk factors, and pre-procedure characteristics will be summarized using descriptive statistics (e.g., mean, standard deviation, n, minimum, maximum) for continuous variables and frequency tables or proportions for discrete variables. Treatments for the randomized subjects will be compared with a chi-square or Fisher exact test for discrete variables and a Student *t*-test for continuous variables. Procedural characteristics will be summarized similarly. No formal statistical testing will be done for the Roll-In, Extended Durability, or CAS subjects. Please see Section **11.1.2** regarding statistical testing for the ACURATE *Prime* XL Nested Registry.

11.1.4. Post-procedure Measurements

Post-procedure information will be collected at regularly scheduled follow-up examinations as detailed in the clinical study schedule (Table 10.1-1) and will be summarized using descriptive statistics for continuous variables (e.g., mean, standard deviation, n, minimum, maximum) and frequency tables or proportions for discrete variables. Estimates will be reported by treatment group and, for randomized subjects (Main Randomized Cohort and Extended Durability Study), differences between treatment groups and their 95% confidence intervals will be presented. Treatments for the randomized subjects will be compared with the chi-square or Fisher exact test for discrete variables and the Student t-test for continuous variables. No inferences are planned on the additional measurements and, therefore, alphaadjustments for multiple comparisons will not be used. The Kaplan-Meier product-limit method will be used to estimate rates for time-to-event endpoints and treatment groups will be compared using the Log-rank and Wilcoxon tests. Adverse event and SAE rates will be reported. No formal statistical testing will be done for the Roll-In, Extended Durability Study, or ACURATE CAS subjects. Please see Section 11.1.1.1 and Section 11.1.2, respectively, regarding statistical testing for the Main Randomized Cohort and the ACURATE Prime XL Nested Registry.

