	physical activity. They are comfortable at rest. Ordinary physical
	activity results in fatigue, palpitation, dyspnea, or anginal pain.Class IIISubjects with cardiac disease resulting in marked limitation of
	physical activity. They are comfortable at rest. Less than
	ordinary physical activity causes fatigue, palpitation, dyspnea, or
	anginal pain.
	Class IV Subjects with cardiac disease resulting in inability to carry on
	any physical activity without discomfort. Symptoms of cardiac insufficiency or of the anginal syndrome may be present even at
	rest. If any physical activity is undertaken, discomfort is
	increased.
NONSTRUCTURAL	Any abnormality not intrinsic to the valve itself that results in stenosis or
DYSFUNCTION	regurgitation of the operated valve or hemolysis. The term nonstructural
	dysfunction refers to problems (exclusive of thrombosis and infection) that do not
	directly involve valve components yet result in dysfunction of an operated valve, as diagnosed by re-operation, autopsy, or clinical investigation. Nonstructural
	dysfunction includes the following.
	• Entrapment by pannus, tissue, or suture
	Paravalvular leak
	• Inappropriate sizing or positioning
	• Residual leak or obstruction after valve implantation or repair
	Clinically important intravascular hemolytic anemia
	• Development of aortic or pulmonic regurgitation as a result of technical errors
	• Dilatation of the sinotubular junction
	• Dilatation of the valve annulus after either valve replacement with stentless
	prostheses, new onset of coronary ischemia from coronary ostial obstruction,
	or paravalvular aortic regurgitation

	Table 23.2-1. Definitions
Term	Definition
OPERATIVE RISK ⁶⁷	Operative risk is determined by a center cardiac surgeon and must be confirmed by the Case Review Committee (including a cardiac surgeon). Low: Estimated 30-day risk of mortality is < 3% Intermediate: Estimated 30-day risk of mortality is 3–10% High: Estimated 30-day risk of mortality is >10–15% Very High: Estimated 30-day risk of mortality is >15% Extreme: Estimated 30-day risk of irreversible morbidity or mortality is ≥50%
PARAVALVULAR REGURGITATION	Leakage due to a separation of the prosthetic valve from the annulus. Any evidence of leakage of blood around the device. Diagnosis of paravalvular regurgitation may be obtained from TEE/TTE, however, definitive diagnosis is obtained at re-operation, explant, or autopsy.

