## 3.1.4 Bayesian Statistical Methods

## 3.1.4.1 Piecewise exponential survival model

The primary endpoint event rates for the hypothesis test specified in Section 3.1.1 will be estimated through posterior probabilities of the hazards from the piecewise exponential survival models. The piecewise exponential models will be constructed by subject operative risk (extreme/high, intermediate, and low). To simplify the notations, the formulas in the Section 3.1.4 represent the general notations within each risk stratum and the same notations can be applied to the data for each risk stratum.

Within each risk stratum, the time partition for the piecewise exponential models between 0-365 days is defined as:

 $0 = t_0 < t_1 < t_2 < t_3 = 365$ , where  $t_1 = 30$  and  $t_2 = 180$ The hazard rates will be estimated for the three intervals:  $\tau_1: [t_0, t_1], \tau_2: (t_1, t_2]$ , and  $\tau_3: (t_2, t_3]$ . The hazard within each time interval is considered as constant by treatment group.

Within each time intervals, the piecewise exponential models will be generated by treatment group (test and control). Let  $\lambda_{j,k}$  denote the hazard rate for subjects in the jth treatment group and the kth time interval, j=1, 2 and k=1, 2, 3, where the indices are defined as the following:

j is for treatment groups (1: test arm, 2: control arm),

k is for the time intervals (1: [0,30], 2: (30, 180], 3: (180, 365]) There will be total six estimated the hazard rates within each risk stratum.

Based on the estimated hazard rates  $\lambda_{j,k}$  from the models, the estimated probability of a subject who is in the jth treatment group developing an event at time  $\tilde{t}$  is defined as:

$$P_{j}(\tilde{t};\lambda_{j,k}) = \begin{cases} 1 - e^{-(\lambda_{j,1}*(\tilde{t}-t_{0}))}, & t_{0} \leq \tilde{t} \leq t_{1} \\ 1 - e^{-(\lambda_{j,1}*(t_{1}-t_{0})+\lambda_{j,2}*(\tilde{t}-t_{1}))}, & t_{1} < \tilde{t} \leq t_{2} \\ 1 - e^{-(\lambda_{j,1}*(t_{1}-t_{0})+\lambda_{j,2}*(t_{2}-t_{1})+\lambda_{j,3}*(\tilde{t}-t_{2}))}, t_{2} < \tilde{t} \leq t_{3} \end{cases}$$

Where  $\lambda_{j,k} = (\lambda_{j,1}, \lambda_{j,2}, \lambda_{j,3}).$ 

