# 3.4 Other Endpoints

Additional analyses at interim for other CEC endpoints will be performed on all enrolled Main Randomized Cohort subjects (N=1500) using the piecewise exponential prediction models specified in Section 3.1.5. Event rates and credible intervals will be provided.

For the Main Randomized Cohort (including 4D-CT Cohort subjects), the 4D-CT Cohort, and the Extended Durability Study, the analysis will be conducted separately. Statistical comparisons for these endpoints will be made between the test and the control arms within each cohort. 4D-CT analysis will include the data for subjects who are eligible for the Main Randomized Cohort analysis at the time of the interim analysis. Analyses for other endpoints will use the standard frequentist methods (details in Section 4.1), such as Chi-square or Fisher's exact for binary variables, T-test for continuous variables, or Log-rank test for time-to-event or Kaplan–Meier survival analysis when they are appropriate, at both the interim and the final analyses. Additional analysis methods may be used when they are appropriated (e.g. Breslow-day test for interaction, ANOVA test or Kruskal-Wallis test for continuous variables, one-sample T-test or McNemar's test for paired analysis).

For the roll-in, the ACURATE *Prime* XL Nested Registry, and the Continued Access Study cohorts, the analyses will be conducted separately, and descriptive analyses will be provided.

Reference:

FDA Guidance for Industry and FDA Staff: Guidance for the Use of Bayesian Statistics in Medical Device Clinical Trials, February 2010

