# 5 ADDITIONAL DATA ANALYSES

# 5.1 Adjudicated CEC Event Analysis

For clinical events, the cut-off for events for 30-day endpoints will be 30 days, for 6month endpoints it will be 180 days, for 1-year endpoints it will be 365 days, and for endpoints at 2–10 years it will be 365 days times the number of years. For events at discharge or 7 days post-procedure, the cut-off for events will be the earlier date of discharge or 7 days post-procedure for each subject. The number of evaluable subjects for the CEC event includes subjects who have CEC confirmed events or are in study at least 23, 150, or 335 days (defined as sufficient follow-up in Section 7.3.3) for 30-day, 6month, or 1-year outcome analysis, respectively. For analysis at 2-10 years, the sufficient follow-up is defined as "number of years times 365 minus 45". The number of evaluable subjects for the CEC event at discharge will include all subjects in the specific analysis set.

The Kaplan-Meier rates for all CEC Events will be provided in analyses at 30 days, 6month, and 1-10 years. The survival analysis (including accumulated event curve) for time-to-event endpoint will be provided for selected CEC events, and log-rank test pvalue and wilcoxon test p-value will be provided for comparing two survival curves.

Event to be analysed include the following:

- o Mortality: all-cause, cardiovascular, and non-cardiovascular
- Stroke: disabling and non-disabling
- Myocardial infarction (MI): periprocedural (≤72 hours post index procedure) and spontaneous (>72 hours post index procedure)
- Bleeding: life-threatening (or disabling) and major (through 5 years)
- Acute kidney injury (AKI; ≤7 days post index procedure): based on the AKIN System Stage 3 (including renal replacement therapy) or Stage 2
- Major vascular complications (through 5 years)
- Repeat procedure for valve-related dysfunction (surgical or interventional therapy)
- Hospitalization for valve-related symptoms or worsening congestive heart failure (NYHA class III or IV)
- New permanent pacemaker implantation resulting from new or worsened conduction disturbances
- New onset of atrial fibrillation or atrial flutter
- Coronary obstruction: periprocedural (≤72 hours post index procedure)
- Ventricular septal perforation: periprocedural ( $\leq$ 72 hours post index procedure)
- Mitral apparatus damage: periprocedural ( $\leq$ 72 hours post index procedure)
- Cardiac tamponade: periprocedural (≤72 hours post index procedure)
- Valve migration

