#### 5.6 Multivariable Analyses

Univariate and multivariate analyses will be performed to assess the effect of potential predictors on the primary endpoint and additional endpoints. The following variables will be analyzed as possible predictors:

Category	Covariates		
Treatment	Treatment group (ACURATE=1 vs Control=0)		
Cohort	4D-CT Cohort		
Demographics and Baseline Characteristics	Age at time of consent, Gender, Race, BMI, NYHA, STS Score, EuroSCORE II, Operative risk		
General Medical History	Medically treated diabetes mellitus, History of hyperlipidemia, History of hypertension, History of peripheral vascular disease, Severe Liver Disease/Cirrhosis, History of Dialysis Dependent Renal Failure, History of Chronic Obstructive Pulmonary Disease, Severe lung disease, Severe pulmonary hypertension		
Cardiac History	History of Coronary Artery Disease, History of Myocardial Infarction, History of congestive heart failure, Prior Balloon Aortic Valvuloplasty, Current Anginal Status, History of Percutaneous Coronary Intervention (PCI), History of Coronary Artery bypass Graft (CABG) Surgery, Hostile Chest, Porcelain Aorta, Prior chest radiation therapy, Neuromuscular disease that creates risk for mechanical ventilation or rehabilitation after surgical aortic valve replacement, Orthopedic disease that creates risk for rehabilitation after surgical aortic valve replacement, History of Atrial Fibrillation, History of Atrial Flutter, Prior Pacemaker Implant		
Neurological History	History of cerebrovascular accident (TIA/Stroke), Right Carotid Artery Stenosis (>= 80%), Left Carotid Artery Stenosis (>= 80%), Prior Carotid Endarterectomy / Carotid Artery Stenting		

#### Form/Template 90702621 Rev/Ver AF ACURATE IDE SAP 92400558, Rev/Ver I Page 45 of 64

Frailty	Time to walk 5 meters, Use of wheelchair, Number of falls in the past months, Maximum Grip Strength Average, Katz Basic Activities of Daily Living Score		
Medications	DAPT at baseline (excluding loading dose), Anticoagulant		
Echo Aortic Factors (Core lab)	Aortic valve area AVA (VTI), Mean Aortic valve gradient, Aortic valve peak velocity, LVEF, Transvalvular aortic regurgitation, Doppler Velocity Index (DVI) (VTI), Systolic pulmonary pressure (sPAP)		
CTA (Core Lab)	Annular area, LVOT area		
Peri-procedural Characteristics	Post-dilation balloon performed		

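### Minor efficiency loss: frequentist event comparisons in the Main Randomized Cohort are not stratified by operative risk, although that factor is recorded for every subject and stratifies the primary model

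*Protocol*

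**What the plan says.** Protocol 11.1.4 covers post-procedure outcomes. For discrete variables: "Treatments for the randomized subjects will be compared with the chi-square or Fisher exact test for discrete variables". For time-to-event endpoints, Kaplan-Meier rates are estimated and "treatment groups will be compared using the Log-rank and Wilcoxon tests". Differences between the randomized arms are reported with 95% confidence intervals. The same section says: "No inferences are planned on the additional measurements".

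SAP 5.1 lists the adjudicated events and plans Kaplan-Meier rates at 30 days, 6 months and 1 to 10 years. For selected events it adds that a log-rank p-value and a "wilcoxon test p-value will be provided for comparing two survival curves". SAP 4.1 sets the general tests, and SAP 3.4 applies them to other endpoints at both the interim and the final analysis. None of these sections names a stratification factor. The composite is not in the SAP 5.1 list, but the wording of Protocol 11.1.4 on time-to-event endpoints is general enough to include it.

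Operative risk is available. Protocol 25.2 says: "Operative risk is determined by a center cardiac surgeon and must be confirmed", with confirmation by the Case Review Committee. SAP 3.1.4.1 builds the primary piecewise exponential models separately for three operative-risk classes (extreme/high, intermediate, low), and SAP 3.1.5.4 combines them with fixed 35/30/35 weights. Randomization (Protocol 11.2.4, SAP 4.4) is stratified by center and intended control device, not by operative risk.

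Two other places bring operative risk in. SAP 3.4: "Additional analyses at interim for other CEC endpoints will be performed on all enrolled Main Randomized Cohort subjects", using the primary's piecewise models. SAP 5.6: "Univariate and multivariate analyses will be performed to assess the effect of potential predictors on the primary endpoint and additional endpoints", with treatment and operative risk among the candidates.

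**The concern.** The tables of death, stroke and rehospitalization will show which component drives the composite and whether any component points to harm. Operative risk is a strong predictor of these events, is collected anyway, and is not balanced by design. An unstratified comparison leaves the between-class variation in the error term and lets chance imbalance in risk add to the noise. The primary result is risk-weighted and the component tables are not, so the two can also describe slightly different patient mixes. What is at stake is the width of intervals and the power of supportive tests, not the trial's conclusion.

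**Working it through.** **The plan's own figure.** The documents give no power for these comparisons. The nearest stated figure is the primary's: power above 90% with 712 evaluable per group (22.3% in both arms, margin 8.0 points, one-sided 0.025). A fixed design needs 569 per arm for 90% power. With Pocock-type spending at 70% information (z bounds 2.059 and 2.252), 712 per arm gives 93.2%. Also 712/0.95 = 749.5, hence 750. The figure reproduces and does not change under this point.

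**Inputs.** From the documents: 750 per arm, risk mix 35/30/35, overall composite rate 22.3%, 1-year cut-off at 365 days. Assumed: the 1-year rate in each class. SAP Table 4 is only a guide. It shows 37% in an extreme-risk study (death, major stroke, rehospitalization) and 8.5% in a low-risk study (death, stroke, rehospitalization). Its high- and intermediate-risk rows omit rehospitalization.

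**Variance of a rate difference.** With class weights w and rates p, the stratified-to-unstratified variance ratio is Σw·p(1−p) / [P(1−P)], where P = Σw·p.

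- At 38/19.5/9%, P = 0.1330 + 0.0585 + 0.0315 = 0.223.
- Within-class variance = 0.35×0.2356 + 0.30×0.1570 + 0.35×0.0819 = 0.1582.
- Total variance = 0.223×0.777 = 0.1733.
- Ratio = 0.913, an 8.7% reduction. Simulated standard errors agree: 0.02144 falls to 0.02050, and (0.02050/0.02144)² = 0.914.
- In subjects, 1500×(1/0.913 − 1) ≈ 143. At the narrower spread of 30/22/15%, the ratio is 0.977 and the figure is about 35.

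**Log-rank power.** Simulation used 3000 trials per row with 1500 subjects, exponential times, censoring at 1 year and two-sided 0.05. Each power entry is unstratified, then stratified.

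| Assumed class rates (extreme-high / intermediate / low) | Overall | Variance ratio | Within-class HR 1.3 | Within-class HR 1.5 |
|---|---|---|---|---|
| 37 / 20 / 9.6% | 22.3% | 0.9227 | 66.7%, 70.6% | 97.1%, 98.3% |
| 30 / 22 / 15% | 22.3% | 0.9771 | 69.3%, 70.4% | 98.1%, 98.3% |
| 16 / 6.7 / 2% (death-like) | 8.3% | 0.9535 | 34.4%, 35.2% | 67.9%, 70.2% |
| 5 / 3 / 2% (stroke-like) | 3.4% | 0.995 | 16.8%, 17.1% | 34.8%, 35.3% |

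The hazard ratios here only define the simulated alternatives; the plan does not estimate one. A separate run of 2000 trials at 38/19.5/9% and HR 1.36 gave 81.6% and 84.9%. For death at 17/8/2% and HR 1.5 it gave 72.3% and 74.8%, and simulated standard errors in that setting (0.01449 and 0.01418) imply about 4% less variance. With no treatment effect at 37/20/9.6%, type I error was 5.1% unstratified and 5.0% stratified.

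**Mix at the interim.** SAP Table 2 assumes 194, 221 and 115 subjects per arm with 1-year data, which is 37/42/22% of 530. At 38/19.5/9% this mix gives (194×0.38 + 221×0.195 + 115×0.09)/530 = 24.0%, against 22.3% under the primary's weights. The shift applies to both arms, so it mainly changes the level of the rates. It changes the difference only if the treatment difference varies by class.

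**The case against.** The strongest reply is that these are supportive tables. The protocol disclaims inference on them, the unstratified tests are valid, and the primary comparison is already risk-stratified. That stands, and it is why the point is minor.

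A second reply is that risk is handled elsewhere. This stands only in part. The risk-stratified model for other adjudicated events is limited to the interim, so at the final analysis and in the later Kaplan-Meier analyses only unstratified comparisons are specified. SAP 5.6 is stepwise selection (univariate p ≤ 0.20, entry and exit at 0.1), which does not force treatment and operative risk into one model. SAP 5.4 summarizes operative-risk subgroups but specifies treatment comparisons only for age, race and gender.

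Several stronger readings are tempting, and the documents do not support them:

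- A reader might infer that hazard ratios will be pulled toward 1. Neither document plans a treatment hazard ratio, and rate or Kaplan-Meier differences are not attenuated by omitting a covariate. Were a hazard ratio reported, 1.30 would become 1.28 to 1.30 and 1.50 would become 1.47 to 1.50. That is a marginal rather than a conditional quantity, not a bias.
- A reader might infer that chance imbalance invalidates the tests. The simulated type I error shows otherwise.
- A reader might take the spread in SAP Table 4 as the stated reason for stratifying the primary. The SAP presents that table to support the relation between hazards in successive time intervals. Its extreme- and low-risk rows also differ in device and in stroke definition.
- A reader might take the 9% figure as expected. It gives the whole extreme/high class 38%, above the table's highest value of 37%, although 25 of that class's 35 percentage points are high rather than extreme risk.

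An objection to the remedy also stands. Three-class estimates are unstable for very rare events, and SAP 4.1 already moves to Fisher's exact test when an expected count is below 5.

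**Conclusion.** The point holds as a minor efficiency improvement. The frequentist comparisons of the composite and adjudicated events in the Main Randomized Cohort forgo precision that a recorded, confirmed baseline factor would supply.

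Under the assumed class rates, the loss is about 2 to 9% of rate-difference variance for the composite. That is worth roughly 1 to 4 points of log-rank power where power is not already near its ceiling. For death it is about 4 to 5% of variance and 1 to 2.5 points. For rare events such as stroke it is under 1%, so stratifying would not materially sharpen a harm signal there. The true gain depends on how far event rates differ between classes, which the documents do not give for these endpoints. Type I error, sample size and the primary conclusion are unaffected.

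**What to change.** In Protocol 11.1.4 and SAP 3.4, 4.1 and 5.1, for the Main Randomized Cohort at interim and final:

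- Add log-rank and Wilcoxon tests stratified by operative risk (extreme/high, intermediate, low).
- Add risk-stratified differences with 95% confidence intervals, using the primary's 35/30/35 weights so that the components match the composite. Mantel-Haenszel weights would follow the observed class sizes and would not match.
- Limit both to the composite, death, stroke, rehospitalization and other events frequent enough in each class, with the threshold set in advance. One option is to apply the SAP's own expected-count rule of 5 class by class. Stroke would be borderline: at an assumed 2% in the low-risk class, 0.35×750×0.02 gives about 5 events per arm.
- Keep the unstratified versions alongside, and Fisher's exact test for rare events.

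The cost is SAP wording and a strata statement, with no new data. The downsides are a second set of results to report and unstable estimates if the method is applied to sparse events. The change should be made before the unblinding at the formal interim that SAP 4.3 describes.
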